#### **15.1.2.** Immune-Related Adverse Events

The FDA approved the drug Yervoy (Ipilimumab), a checkpoint blockade immunotherapy for the treatment of Melanoma. The immune mechanism of this drug is novel and resulted also in novel immune-related adverse events. Since the immune mechanism of Yervoy and other drugs of this class may be similar to the mechanism of the Study Drug, the Investigators should be particularly vigilant in diagnosing and reporting Immune-Related Adverse Events.

The manufacturer of Yervoy has provided literature to assist physicians in identifying immune-related adverse events. This literature might serve as a guide to investigators as to the types of adverse events that might occur with drugs that have an immune mechanism of action.

#### 15.1.3. Expected Adverse Events

Expected AEs are any AEs whose nature and severity have been previously observed and documented (in the Investigator Brochure) for the study drug. Expected AEs should not be reported to the IRB/EC.

The following adverse events are known to be associated with the administration of AlloStim®.

- Allergy, Immunology Reaction
- Flu-like Symptoms
- Pain-NOS

The following adverse events have been observed but have not been attributed to the study drug as they may be related to the underlying disease:

- Hemoglobin (Low)
- Lymphopenia (Low Abs. Lymphs)
- Alkaline phosphatase (High)
- AST (High)
- Calcium (Hypocalcemia)
- Hypoalbunemia (Low Albumin)
- DVT (deep vein thrombosis) or other thrombolic events

In addition, subjects in trials enrolling patients who failed two treatment lines with no available treatment options (such as the subjects in the current study) are expected to die from their disease.

#### AEs do not include the following:

- Medical surgical procedures are not AEs (e.g., surgery, endoscopy, tooth extraction, transfusion). The condition that leads to the procedure is an AE if the procedure was not planned at screening visit.
- Overdose of concomitant medication without any signs or symptoms unless the subject is hospitalized for observation.
- Hospitalization for elective surgery planned prior to study (situation where an untoward medical occurrence has not occurred).

AEs will be solicited from physical exam, subject and caregiver/family interview in person or by telephone and laboratory test results. The investigator is to report all directly observed adverse events and all adverse events spontaneously reported by the trial subject or caregiver/family member. Each trial subject will be questioned about adverse events at each clinic visit following initiation of treatment and by telephone at least once a month during the follow-up phase. The question asked should be, "Since your last clinic visit have you had any health problems?", or a similar type of open-ended query.

For all AEs, the investigator must pursue and obtain information adequate both to determine the outcome of the AE, and to assess whether it meets the criteria for classification as a serious adverse event (SAE). For all AEs, sufficient information should be obtained by the investigator to determine the causality of the AE (i.e., investigational product or other illness). The investigator is required to assess causality and indicate that assessment on the CRF/eCRF. Follow-up of the AE is required if the AE persists. Follow-up is required until the event is resolved or stabilized at a level acceptable to the investigator and the Sponsor's medical monitor or his/her designated representative.

AE severity will be recorded and graded according to the National Cancer Institute (NCI) Common Terminology Criteria for Adverse Events (CTCAE) version 4.03 (June 14, 2010) and coded into the database according to the latest version of MedDRA.

 Table 7
 Severity of Adverse Events According to CTCAE (Version 4.03)

| Grade | Description   |
|-------|---|
| 0     | No AE or within normal limits   |
| 1     | Mild; asymptomatic or mild symptoms; clinical or diagnostic observations only; intervention not indicated.  |

| Related      | The time sequence of drug intake and event is reasonable                   |
|              | The AE is more likely explained by the study drug than by another cause    |
|              | The event corresponds to what is known about the drug                      |
|              | A direct cause and effect relationship between the suspected drug and the  |
|              | AE has been demonstrated   |
|              | The event ceases or diminishes upon stopping drug intake or diminishes     |
|              | during the interval before rechallenge (dechallenge)                       |
|              | The event resumes upon restarting drug intake (rechallenge)                |
| Probably     | There is evidence of exposure to the study drug.                           |
| Related      | The time sequence of drug intake and event is reasonable                   |
|              | The event corresponds to what is known about the drug                      |
|              | The AE is more likely explained by the study drug than by another cause    |
|              | The event ceases or diminishes upon stopping drug intake or diminishes     |
|              | during the interval before rechallenge (dechallenge)                       |
|              | The effect of rechallenge is unknown or does not elicit or exacerbate the  |
|              | event  |
| Possibly     | There is evidence of exposure to the study drug.                           |
| Related      | The time sequence of the drug intake and event is reasonable               |
|              | The event corresponds to what is known about the drug                      |
|              | The effect either remains or continues to exacerbate after dechallenge     |
|              | No change occurs after rechallenge   |
|              | The AE could have been due to another equally likely caus                  |
| Unlikely     | There is evidence of exposure to the study drug. However, it does not      |
|              | follow a reasonable temporal sequence from administration of drug; or      |
|              | The event does not correspond to what is known about the drug; or          |
|              | The effect either remains or continues to exacerbate after dechallenge and |
|              | no change occurs after rechallenge; or                                     |
|              | There is another more likely cause of the AE                               |
| Not Related  | The subject did not receive the study drug; or                             |
|              | The temporal sequence of the AE onset relative to administration of the    |
|              | study drug is not reasonable; or   |
|              | There is another obvious cause of the AE                                   |

Table 8Causality of Adverse Event

Outcome to Date are classified as follows:

- Recovered/Resolved: The subject has fully recovered from the AE with no residual effects observable
- Recovered/Resolved with sequelae: The subject has recovered from the AE with residual effects observable

- Improved: The subject status improved but has not been fully recovered
- Ongoing: AE is not recovered/not Resolved
- Fatal
- Unknown

AEs will be coded using the latest version of the Medical Dictionary for Regulatory Activities (MedDRA) AE dictionary.

All AEs, serious and not serious, will be recorded on the AE CRF page, and if relevant, the Concomitant Medications Record in the CRF will be updated. Particular attention should be made to ensure no discrepancies between the AE and the SAE form (i.e. outcome, severity, relationship must be consistent).

# **15.2.** SERIOUS ADVERSE EVENTS

A Serious Adverse Event (SAE) is an untoward medical occurrence, regardless of whether or not it is considered related to the study medication. Seriousness (not severity) serves as a guide for determining if an AE qualifies as a SAE.

The following must be reported as SAE:

- Death (regardless of the cause) while on treatment that occurs during the safety evaluation period, including deaths due to disease progression.
  - Deaths occurring after the Safety Evaluation Period need not be reported as SAE unless they are a result of an event that started while on treatment during the Safety Evaluation Period.
- A life-threatening AE (e.g., the patient was at immediate risk of death from the event as it occurred) should be reported as SAE. This does not include an event that, had it occurred in a more serious form, might have caused death.
- In-patient hospitalization or prolongation of existing hospitalization
  - Excluding hospitalizations for:
    - administration of the investigational product or procedures required by the study protocol or tumor-related diagnostic procedures
    - other planned hospitalization
    - social reasons and respite care in the absence of any deterioration in the subject's general condition
  - Emergency room visits do not automatically qualify as SAE. Treatments in the emergency room for procedures such as hydration that did not require admitting the patient to the hospital are not considered a SAE, but should be reported as AE.
- A Persistent or significant disability/incapacity.

Important medical events that may not result in death, be life-threatening, or require hospitalization may be considered SAE drug experiences when, based upon appropriate medical judgment, they may jeopardize the patient and may require medical or surgical intervention to prevent one of the outcomes listed in this definition.

An event need not be reported as SAE if it exclusively represents a relapse or an expected change or progression of the baseline malignant disease. This type of event needs only to be reported as AE.

Pre-planned hospitalizations or procedures for pre-existing conditions that are already recorded in the subject's medical history at the time of study enrollment will not be considered SAEs.

Any newly emergent SAEs, after treatment is discontinued or the subject has completed the study, and is considered to be related to the study drug or study participation, should be recorded and reported immediately to the Sponsor. The post-study period for the purpose of SAE reporting is up to 30 days following last IV booster administration.

#### 15.2.1. Definition of an Unexpected Adverse Event

An **unexpected** adverse drug event is any AE, the specificity or severity of which is not consistent with information in the current Investigator's Brochure (IB) for an unapproved investigational product.

**Serious Unexpected Suspected Adverse Reaction (SUSAR)** is a SAE assessed as unexpected by the Sponsor and that is judged by either the reporting investigator or the Sponsor to have a reasonable causal relationship to a medical product.

#### 15.2.2. Handling of Serious Adverse Events

For all SAEs, the investigator is obligated to pursue and provide information as requested by the Sponsor's clinical monitor or designated representative in addition to that on the CRF/eCRF. In general, this will include a description of the SAE in sufficient details to allow for a complete medical assessment of the case and independent determination of possible causation. Information on other possible causes of the event, including concomitant medications and illnesses must be provided. The investigator's assessment of causality must also be provided. If causality is unknown, it should be indicated. In the case of a subject death, a summary of available autopsy findings must be submitted as soon as possible to the Sponsor or its designated representative. The investigator should ensure that information reported immediately by telephone or other means and information entered in the CRF/eCRF are accurate and consistent.

Any SAE or death must be reported immediately to the Sponsor, independent of the circumstance or suspected cause, if it occurs or comes to the attention of the investigator at any time during the study through the last follow-up visit required by the protocol. Any SAE occurring at any other time after completion of the study must also be promptly reported if a causal relationship to the investigational product is suspected.

Any AEs classified as "serious" must be recorded on the AE/SAE CRF/eCRF and require expeditious handling and reporting to Sponsor to comply with regulatory requirements, independent whether considered related or unrelated to the study therapy. These SAEs will include the immediate cause of deaths, regardless of their causal relationship to the investigational product. All SAEs must be reported using the AE/SAE Form. To the extent possible, the descriptive terminology and other SAE attributes entered on the form should approximate similar information in the CRF/eCRF. The completed form must be faxed/emailed to the sponsor within 24 hours of the study site personnel's initial notification/awareness of the event, even if only limited information is available. Preliminary or supplemental SAE information captured on the clinic note, concomitant report, and laboratory report, may alternatively be scanned and transmitted to the Sponsor or designee. The authorized study site personnel may sign completed AE/SAE forms. The investigator signs each final SAE report. The original AE/SAE form must be kept on file at the study site. Protocol Date: December 23, 2014 Amendment Date: September 12, 2017 Page 66 of 94

Collection of complete information concerning SAEs is extremely important. Thus, follow-up information that becomes available as the SAE evolves, as well as supporting documentation (e.g. hospital discharge summaries, additional laboratory and test results, autopsy reports, etc.), should be collected subsequently, if not available at the time of the initial report, and immediately sent to the Sponsor or designee using the same procedure as the initial SAE report.

Follow-up of all SAEs that occur during the study will continue until their satisfactory resolution or stabilization. In outstanding cases, it may be defined as "ongoing without further follow-up" by the Investigator's and Sponsor's joint decision.

A follow-up SAE Report Form must be completed by the site (marked as "follow-up report") and emailed within 24 hours to the sponsor ([contact]). A SAE follow-up report is required whether or not there is any additional information to the initial report.

As for the initial SAE report, once faxed/emailed, the follow-up SAE report and accompanying documentation should be placed in the SAE section of the Investigator's site file.

For ease of analysis, worldwide standardization, and regulatory reporting, Sponsor or designee will code each reported SAE or symptom to its corresponding preferred term and system organ class in the Medical Dictionary for Regulatory Activities (MedDRA®). The NCI-CTCAE Version 4.03 will serve as the reference document for determining/grading the severity or toxicity grade of all SAEs and other symptoms.

For SAEs whose toxicity grading is not contained within the NCI-CTCAE Version 4.03 toxicity criteria, the Principal Investigator will be responsible for assessing severity based on the intensity of the event as it presented. Investigators and study site personnel enter the SAE term on the CRF/eCRF and AE/SAE form as accurately as possible, regardless of the NCI-CTCAE Version 4.03 terminology for the event.

15.2.1. Exceptions in the Reporting of Serious Adverse Events

According to EU Detailed guidance on the collection, verification and presentation of adverse reaction reports arising from clinical trials on medicinal products for human use, ENTR/CT3, 5.1.9, regarding clinical trials in high morbidity or mortality diseases, it is acceptable to define some exceptions in the immediate reporting of specific SAEs.

Metastatic colorectal cancer is a recognized condition with high morbidity and/or high mortality.

Under these circumstances, it seems appropriate that the SAEs, clearly related to the MCRC (i.e. disease-related) could be an exception for an immediate systematic reporting.

These AEs will be thoroughly handled and followed up through the CRF (AE form) and will be reviewed monthly by the sponsor's medical monitor and could be re-qualified for reporting if necessary.

Each event must be carefully analyzed by the Investigator to decide whether the SAE could be considered as an exception or must be immediately reported.

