# **Toxicity Monitoring**

Two types of toxicity are assessed for determination of whether a Dose Limiting Toxicity (DLT) has occurred. An acute dose limiting toxicity (ADLT) is assessed within 48h of a dose administration during the priming, vaccination and activation steps of each protocol. Cumulative dose limiting toxicity (CDLT) is assessed during the complete Safety Evaluation Period including any ADLT that occurs in the booster dosing.

An ADLT is defined as the occurrence of any of the following within 48h of dosing:

- Any  $\geq$  Grade 3 local injection site reaction;
- Any  $\geq$  Grade 3 graft vs host disease;
- Any  $\geq$  Grade 3 infusion related symptoms of duration > 2 days;
- Any  $\geq$  Grade 4 infusion reaction of any duration

For any Grade 1-2 acute toxicity, the study drug administration schedule can continue to the next scheduled dose. If an ADLT is observed, the subject will be followed until the toxicity is resolved or the subject is stable. No further dosing for that subject will occur after an ADLT event

A CDLT event is defined as the occurrence of any of the following within the Safety Evaluation Period

- Any  $\geq$  Grade 3 graft vs. host disease
- Any toxicity  $\geq$  Grade 3 that is probably or definitely related to the study drug;
- Any toxicity not present at baseline that occurs at  $\geq$  Grade 4
- Any autoimmune toxicity  $\geq$  Grade 3 not present at baseline

All adverse events (AEs) and serious adverse events (SAEs), regardless of attribution to the study drug, will be coded, graded and become part of the final safety report for each cohort. The DSMB will review the safety data on each cohort and recommend whether to advance enrollment to the next cohort.

The development of any Grade 4 or greater toxicity in any subject at any time will prompt a review of safety data by the Sponsor, PI and the DSMB prior to accrual of any additional subjects. It is recognized that Grade 4 events and death can occur in this population due to disease progression. Therefore, dosing will continue for currently enrolled subjects at the occurrence of a grade 4 event according to protocol unless the PI determines the event is definitely or probably related to the study drug. If attribution is assigned to the study drug dosing will be suspended pending review by DSMB.

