#### **15.3.** Adverse Events Reporting

#### 15.3.1. Reporting Requirements

- The adverse events reporting period for this trial begins upon receiving the first dose of investigational product and ends on the last day of the Safety Evaluation Period.
- All adverse events that occur in trial subjects during the adverse events reporting period specified in the protocol must be reported to the Sponsor, whether or not the event is considered study medication related.
- In addition, any known untoward event that occurs subsequent to the adverse events reporting period that the investigator assesses as possibly related to the study medication should also be reported as an AE.
- The investigator also should comply with the IRB/IEC procedures for reporting any other safety information.
- All AEs should be reported to the Sponsor within 10 calendar days.
- All SAEs must be reported to Sponsor immediately (within 24 hours) upon knowledge.
- The Sponsor shall forward these AE reports to the Data Safety Monitoring Board.
- The Sponsor shall forward all SAE reports to the Data Safety Monitoring Board immediately upon receipt.

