#### **15.7.** STOPPING RULES

An external DSMB will oversee this study. The investigators and representatives of the Sponsor and DSMB will review and discuss subject data for all subjects enrolled by teleconference. The DSMB could recommend stopping the clinical trial for safety purposes.

The development of dose limiting toxicity (DLT) in any subject will prompt a review of safety data by DSMB. The development of any DLT toxicity in  $\geq 33\%$  of the accumulated number of subjects at any dosing during the assessment period (28 days after last booster infusion) will result in protocol discontinuation. However, if DTLs only occur in the Activation or Booster phase, then a decision by DSMB may be made to continue enrolling subjects to receive only priming and in-situ vaccination phases.

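### The safety-reporting clocks conflict with each other and do not match the reviews they feed, so accrual can occur before the Sponsor and DSMB know of a Grade 4 or higher event

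*Combined protocol and SAP*

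**What the plan says.** Sections 15.2.2 and 15.3.1 set one rule for serious events. They go to the Sponsor immediately, and in any case within 24 hours, "independent whether considered related or unrelated to the study therapy". Section 15.2.2 says the same of any death. Section 15.2 includes fatal progression in its list of mandatory SAEs: "Death (regardless of the cause) while on treatment that occurs during the safety evaluation period, including deaths due to disease progression".

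Two other passages point the other way. Section 15.2 also says: "An event need not be reported as SAE if it exclusively represents a relapse" or expected progression of the cancer, in which case an AE entry is enough. The section on exceptions (the second of two numbered 15.2.1) says of SAEs clearly related to the cancer, "i.e. disease-related) could be an exception for an immediate systematic reporting". These are handled on the AE form and "will be reviewed monthly by the sponsor's medical monitor and could be re-qualified for reporting if necessary". The investigator decides case by case, and the section does not exclude deaths or Grade 4 events.

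For everything else, Section 15.3.1 says: "All AEs should be reported to the Sponsor within 10 calendar days". Section 15.3.4 asks for AE reports every 10 days. The Sponsor must forward SAE reports to the DSMB at once, but AE reports have no forwarding deadline. Under Section 15.6 the DSMB's automatic alert is set off by an SAE report, and its routine data arrive quarterly.

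Two reviews depend on this flow. In Sections 3 and 8, a toxicity of Grade 4 or higher, whoever has it and whenever it occurs, "will prompt a review of safety data by the Sponsor, PI and the DSMB prior to accrual of any additional subjects". The same paragraph accepts that progression can cause such events, but uses this only to let dosing continue. Section 15.7 says: "The development of dose limiting toxicity (DLT) in any subject will prompt a review of safety data by DSMB".

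**The concern.** A site holding a progression death, or a Grade 4 event it attributes to disease, has two instructions. One says 24 hours whatever the cause. The other allows the AE form. The 24-hour sections do not refer to the exception, and the exception does not say which events stay outside it.

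The exception is also defined by attribution, while the accrual review it feeds ignores attribution. A second gap concerns DLTs. Their definitions in Sections 3 and 8 do not require seriousness, so a Grade 3 injection-site reaction, a related Grade 3 toxicity or a new Grade 4 laboratory value can be a DLT without being an SAE. No DLT-specific clock exists.

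At stake is whether the Sponsor and DSMB can do the reviews the plan assigns to them. Safety is the primary endpoint, Part 1 has about 6 subjects, and single events decide 3+3 cohort advancement and count in the 33% discontinuation rule.

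**Working it through.** The plan states no figure on this point, so there is none to reproduce. The check sets each route against the review it feeds, then sizes the delay.

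**1. Routes by type of event**

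| Event | Clock to the Sponsor | Route to the DSMB | Review it feeds |
|---|---|---|---|
| SAE, not excepted | 24 h (15.2.2, 15.3.1) | Immediate, with automatic alert (15.3.1, 15.6) | Accrual review if Grade 4 or higher; DLT review if a DLT |
| Progression death in the Safety Evaluation Period | 24 h under 15.2, 15.2.2 and 15.3.1; AE form if excepted | Immediate, or no deadline | Accrual review |
| Other disease-attributed Grade 4 SAE | 24 h, or AE form if excepted | Immediate, or no deadline | Accrual review |
| Non-serious Grade 4 laboratory event | 10 days (15.3.1, 15.3.4) | No deadline | Accrual review, and DLT review if not present at baseline |
| Non-serious Grade 3 DLT | 10 days | No deadline | DLT review, 33% rule, and 3+3 if an ADLT |

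Rows 2 and 3 are the contradiction. Rows 4 and 5 are the gap.

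**2. Which clock applies to an excepted SAE.** It stays an AE on the AE form, and Section 15.3.1 gives all AEs 10 calendar days. I therefore use 10 days for Sponsor receipt. The month in the exceptions section is the interval for medical-monitor review and re-qualification.

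**3. Accrual during the delay.** The input is about one subject every two weeks (Section 3, Study Duration). Expected accruals = days / 14.

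- 24 hours: 1/14 = 0.07
- 10 days: 10/14 = 0.71

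If arrivals are Poisson (an assumption), P(at least one) = 1 − exp(−days/14):

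- 24 hours: 1 − exp(−0.071) = 7%
- 10 days: 1 − exp(−0.714) = 51%

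With regular 14-day spacing and random phase, the 10-day probability is 10/14 = 71%.

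**4. Sensitivity to the accrual rate**

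| One subject per | Expected in 24 h | Expected in 10 days | P(at least one) in 10 days |
|---|---|---|---|
| 7 days | 0.14 | 1.43 | 76% |
| 14 days | 0.07 | 0.71 | 51% |
| 21 days | 0.05 | 0.48 | 38% |
| 28 days | 0.04 | 0.36 | 30% |

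These figures cover the time to Sponsor receipt only. The further step to the DSMB cannot be sized, because no deadline is given.

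**5. Effect on the 33% rule.** One DLT in 3 accumulated subjects is 1/3 = 33.3%, which meets the limit; one in 4 is 1/4 = 25%, which does not. The plan does not give the date at which the denominator is counted. If it is counted on receipt of the report, one intervening accrual changes the result.

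**The case against.** The strongest reply is that the pause runs from the event, not from the report. The study is single-center, the PI is one of the named reviewers, and enrollment needs both PI and Sponsor agreement (Section 11.1). A PI who knows of a Grade 4 event is already bound to hold accrual. This stands. A reader might infer that accrual continues after a trigger, or that the breach would be invisible. The documents support neither: Sections 3 and 8 forbid such accrual, and enrolling after a known Grade 4 event would plainly violate them. What remains is that the required review also belongs to the Sponsor and DSMB, who cannot review an event they have not received.

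A second reply is that the clocks are a general rule plus an exception, and that Section 15.2 can be read consistently: deaths are always SAEs, and other pure progression events need not be. That is an available reading of Section 15.2. It does not settle whether the exceptions section removes a progression death or a Grade 4 event from the 24-hour clock.

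Third, Grade 4 is defined by life-threatening consequences, and life-threatening AEs are SAEs. Most clinical Grade 4 events that are not excepted are therefore on the 24-hour clock. This also stands, and it narrows the non-serious part of the accrual gap mainly to laboratory events.

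Other stronger readings are tempting but unsupported:

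- That the monthly cycle lets about 2 subjects accrue (30/14 = 2.1) before the Sponsor hears. The month governs review, and the AE itself is due in 10 days.
- That every DLT pauses accrual. Section 15.7 requires DSMB review of a DLT; the explicit pause attaches to Grade 4 or higher.
- That a Schedule A-2 subject could receive 4 doses (Days 0, 3, 7, 10) because of the delay. Sections 3 and 8 continue dosing of enrolled subjects unless the PI attributes the event to the drug, so suspension turns on attribution, not on the report.
- That Grade 3–4 bilirubin in 7 of 42 subjects (5 + 2) of the earlier study shows the risk. That count is regardless of causality, in a mixed-tumor study with liver listed as a tumor location in 22 of 42, and shows no late report.
- That progression cannot be told from immune flare. Sections 9.2 and 11.2.4 concern RECIST imaging and offer biopsy and irRC to separate the two.

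**Conclusion.** The point holds in limited form. The reporting sections contradict each other for disease-attributed SAEs, most clearly for progression deaths, and the exception is not aligned with an accrual review that ignores cause. DLTs and Grade 4 laboratory events that are not serious have no clock shorter than 10 days and no deadline to the DSMB.

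Accrual can therefore occur before the Sponsor and DSMB know of a Grade 4 or higher event. The expected number is about 0.7 subjects in 10 days (0.36 to 1.43 at one subject per 28 to 7 days), against 0.07 in 24 hours. DLTs that count in the 3+3 and 33% rules can also reach the DSMB late. The sizes rest on the projected accrual rate, on the full 10 days being used, and on accrual not being held by the PI in the meantime. The contradiction itself rests on the text alone. This should be fixed, but it does not show that the pause rule will be breached.

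**What to change.** Reconcile Sections 15.2, 15.2.1 (exceptions), 15.2.2, 15.3.1 and 15.3.4 with the accrual review in Sections 3 and 8 and with Section 15.7:

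- State in the exceptions section and in Section 15.3.1 that the exception does not apply to deaths, Grade 4 or higher events, or DLTs in the Safety Evaluation Period.
- State that these events go to the Sponsor and the DSMB on the existing 24-hour clock, whatever their seriousness or attribution.
- Align the progression sentence in Section 15.2 with this. Other pure progression events can stay on the AE form.
- Add a Grade 4/DLT tick-box to the existing 24-hour form.

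The cost is amendment wording, one form field, and some extra expedited forms in at most about 31 subjects (6 + 25). No dose, schedule or treatment rule changes.
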